12.4 Compensation for injury

The Sponsor and/or Investigator has a liability insurance which is in accordance with relevant legislation. In the event of any suffering, deterioration in health or well-being or any harmful susceptibility or toxicity caused to subjects' participation in the trial, the subject will receive appropriate compensation irrespective of the question of legal liability.

The Sponsor and/or Investigator has an insurance which is in accordance with the legal requirements in the participating countries. This insurance provides cover for damage to research subjects through injury or death caused by the study. The insurance applies to the damage that becomes apparent during the study or within 4 years after the end of the study. Each partner will ensure proper insurance to cover their liability, and damage for subjects participating in their country.

12.5 Incentives

Patients participating in this trial will receive compensation for travelling costs if extra visits to the treating centre (outside of regular care) are necessary.

13. ADMINISTRATIVE ASPECTS, MONITORING AND PUBLICATION

13.1 Handling and storage of data and documents

13.1.1 Data Handling

Subject medical information obtained by this study is confidential, and disclosure to third parties other than those noted below is prohibited. With the subject's permission, medical information may be given to his personal physician or other appropriate medical personnel responsible for his/her welfare.

The information required by the protocol into is entered into an electronic data collection system (EDC). The eCRF data are to be considered source data in addition to the automatic print outs as well as patient records.

The eCRF will be developed by the data manager for the study. Detailed information on the eCRF completion will be provided during the site initiation visits. Each site will also be provided with an eCRF completion manual. In general, all users who have access to the EDC system will be trained. The access to the eCRF is password controlled. Plausibility checks will be performed according to a data validation plan. Inconsistencies in the data will be queried to the investigators via the electronic data collection system; answers to queries or changes of the data will directly be documented in the system. After all data are entered and all queries are solved, the database will be closed.

Data generated by this study must be available for inspection by representatives of other national and local health authorities, the sponsor, and the IRB/IEC for each study site, if appropriate.

Subjects will be identified on CRFs and other documents submitted to the Sponsor or organisations working on behalf of the Sponsor by their subject number, not by name or initials. Documents not to be submitted to the Sponsor or organisations working on behalf of the Sponsor that identify the subject (e.g., the signed informed consent) must be maintained in confidence by the Investigator.

13.1.2 Data Coding

All subjects who sign a study informed consent will be assigned a unique subject identification number at the time of their Screening visit (after consent). Subjects will be identified by this unique subject identification number for the duration of their participation in the study.

All subjects enrolled must be identifiable throughout the study. The Investigator will maintain a list of subject numbers and subject names to enable records to be found at a later date. Subjects will be assigned identification numbers automatically via the eCRF.

The unique subject identification number consists of a combination of numbers: the first number is the land code, followed by the site number and the patient number. For example: in the Netherlands (land code 1) in the first site (site number 01), the first patient (patient number 001) will have the unique subject identification number 101001.

13.1.3 Data Confidentiality

The Investigator is required to ensure that any documents or data given to the Sponsor or its representatives do not contain information that would affect the anonymity of the subjects. The Investigator will obtain permission for direct access to subject data from the subject as part of the written informed consent procedure. This gives permission to examine, analyse, verify, and reproduce any records and reports that are important to the evaluation of the trial. Any party (e.g., domestic and foreign regulatory authorities, Sponsor personnel or its representatives, and auditors) with direct access must take all reasonable precautions, within the constraints of the applicable regulatory requirement(s), to maintain the confidentiality of the subject's identity and Sponsor's proprietary information.

13.1.4 Data Storage

Each research site will retain copies/originals of the approved trial or study protocol, subjects' participation agreements, relevant source documents and all other supporting documentation related to the trial or study for a period of fifteen (15) years. These documents should be retained for a longer (or shorter) period however if required by the applicable regulatory requirements or by an agreement with the Sponsor.

The Sponsor will provide each Investigator with information concerning the current status of the investigational drug as this may relate to the above stated obligation for the retention of study records. The Sponsor will inform each study site as to when these documents no longer need to be retained. Study sites should contact the Sponsor prior to disposing of or archiving any such records.

13.2 Monitoring and Quality Assurance

More information about monitoring can be found in chapter 10.5.

13.3 Amendments

A 'substantial amendment' is defined as an amendment to the terms of the IEC application, or to the protocol or any other supporting documentation, that is likely to affect to a significant degree:

- the safety or physical or mental integrity of the subjects of the trial;
- the scientific value of the trial;
- the conduct or management of the trial; or
- the quality or safety of any intervention used in the trial.

All substantial amendments will be notified to the IEC and to the competent authority. Non-substantial amendments will not be notified to the accredited IEC and the competent authority, but will be recorded and filed by the sponsor.

13.4 Annual progress report

The sponsor/investigator or CRO representative will submit a summary of the progress of the trial to the accredited IEC once a year. Information will be provided on the date of inclusion of the first subject, numbers

of subjects included and numbers of subjects that have completed the trial, SAEs/serious adverse reactions, other problems, and amendments.

13.5 End of study report

The sponsor will notify the accredited IEC and the competent authority of the end of the study within a period of 90 days. The end of the study is defined as the last patient's last visit.

In case the study is ended prematurely, the sponsor will notify the accredited IEC and the competent authority within 15 days, including the reasons for the premature termination.

Within one year after the end of the study, the investigator/sponsor will submit a final study report with the results of the study, including any publications/abstracts of the study, to the accredited IEC and the Competent Authority.

13.6 Public disclosure and publication policy

The final report will be written in English in a Word format and its structure will follow a template based upon the ICH E3, guidelines unless otherwise specified by the sponsor during financial agreement.

Suggested inclusions in the report are: study objectives, materials and methods (including any deviations from the study protocol), evaluation of the study results, observations by the investigator as to the value of the study drug per se, and a discussion of all adverse experiences with interpretation by the investigator as to the study drug involvement.

All information concerning the tested drug and the sponsor's operation, such as patent applications, formulae, manufacturing processes, basic scientific data and formulation information supplied by the sponsor and not previously published are considered confidential and shall remain the sole property of the sponsor. The investigator agrees to use this information only in accomplishing this study and will not use it for other purposes without written consent from the sponsor.

It is understood by the investigator that the information from the clinical study will be used by the sponsor in connection with the development of the tested drug and, therefore, may be disclosed as required to other clinical Investigators or to government agencies. In order to allow for the use of the information derived from the clinical studies, it is understood that there is an obligation to provide the sponsor with complete test results and all data developed in the study.

The trial drug and the information in this document and in any future information supplied contain trade secrets and commercial information that are privileged or confidential and may not be disclosed unless such disclosure is required by law or regulations.

In any event, persons to whom the information is disclosed must be informed that the information is privileged or confidential and may not be further disclosed by them.

Publication rules will be consistent with local regulation and will be addressed in the study contract and should not be in contradiction with the text in the protocol.

Furthermore, a trial publication policy will be formulated by the GLORIA Study Consortium by the end of 2015.

15. APPENDICES

- Appendix A: Schedule of assessments
- Appendix B: Joint counts
- Appendix C: Calculation of DAS28 and DAS44; EULAR response; ACR improvement
- Appendix D: Sharp/van der Heijde damage score
- Appendix E: Patient global assessment and stiffness
- Appendix F: Physician global assessment
- Appendix G: (M)HAQ – (Modified) Health Assessment Questionnaire
- Appendix H: RAID – RA Impact of Disease
- Appendix I: Cost Questionnaire
- Appendix J: EQ-5D – EuroQoL in 5 dimensions
- Appendix K: SF36 – Short Form 36-item Health Survey
- Appendix L: Patient symptom list
- Appendix M: Education level and Baseline prognostic factors

15.1 Appendix A:

Schedule of assessments

	Base-line	2 year treatment period										Follow up / taper
		1	2	3	4	5	6	7	8	9	10	
Visit No	1											
Month (visit window +/- 2 months)	0	3	6	9	12	15	18	21	24^{LV}		27	
Location	clinic	clinic	clinic	remote	clinic	remote	clinic	remote		clinic		clinic
Written informed consent	X											
In- / exclusion criteria	X											
Demographics, education & medical history	X											
Baseline prognostic factors: adherence, health literacy, arthritis helplessness index	X*											
Randomization	X*											
Physical examination	X											
Height	X										X	
Vital signs / weight	X	X	X			X		X		X	X	
AE evaluation (inc. surgery, comorbidity)		X*	X*	X*	X*	X*	X*	X*	X*	X*	X*	
Concomitant medication	X	X	X	X	X	X	X	X	X	X	X	
Lab (hematology ¹ , chemistry ²)	X	X	X			X		X			X	
Lab lipids ³	X	X				X ³					X	
Lab CRP, ESR	X	X	X			X		X		X	X	
Joint counts (44)	X										X	
Joint counts (28)		X	X			X		X			X	
DEXA either with VFA, or without VFA plus X-lat spine (thor, lumb) ^{4,5}		X									X	
X-rays hand and forefeet ⁴	X										X	
Patient global assessment, stiffness duration, stiffness severity	X	X	X	X	X	X	X	X	X	X	X	
Physician global assessment	X	X	X			X		X		X	X	
Questionnaires:												
- RAID	X*	X*	X*	X*	X*	X*	X*	X*	X*	X*	X*	
- full HAQ-DI (24 items)	X*	X*	X*		X*		X*				X*	
- MHAQ-DI (10 items)				X		X		X				
- Cost questionnaire	X*	X*	X*		X*		X*				X*	
- EQ-5D	X*	X*	X*	X*	X*	X*	X*	X*	X*	X*	X*	
- SF36	X*										X*	
- Patient symptom list	X*										X*	
GC or placebo, dispense adherence	X*	X*	X*	X*	X*	X*	X*	X*	X*	X*		

* procedures not belonging to standard of care

^{lv} End of study visit. This visit also needs to be completed by subjects who early terminated the trial.

Apart from CRP and ESR, the following standard of care lab tests will be done on peripheral blood samples.

Lab results of CRP and ESR no more than 4 weeks old may be used for the baseline visit.

Results of the below tests ^{1, 2, 3} no more than 2 months old may be used for the baseline visit:

1) Hemoglobin, Mean Cell Volume, White blood cell count, White blood cell differential count, Platelet count.

2) Glucose (non-fasting), Creatinine, Alanine Aminotransferase;

3) Total cholesterol, HDL cholesterol. Optional for month 12.

4) For the baseline visit: DEXA, DEXA VFA and X-ray images with a maximum of 6 months before or until 3 months after the baseline visit may be used.

5) If possible a whole body DEXA may be performed.

15.2 Appendix B:
Joint counts

	RIGHT		LEFT	
	Pain	Swelling	Pain	Swelling
	0= not tender 1= tender on palpation 2= tender, patient winces 3= tender, patient winces, tries to withdraw	0=no 1=yes	0= not tender 1= tender on palpation 2= tender, patient winces 3= tender, patient winces, tries to withdraw	0=no 1=yes
Cervical spine		---	---	---
Jaw				
Sternoclavicular				
Acromioclavicular				
Shoulder				
Elbow				
Wrist				
MCP I				
MCP II				
MCP III				
MCP IV				
MCP V				
PIP I				
PIP II				
PIP III				
PIP IV				
PIP V				
Hip		---		---
Knee				
Ankle				
Subtalar				
Midtarsal				
MTP I				
MTP II				
MTP III				
MTP IV				
MTP V				

MCP = Metacarpophalangeal; MTP = metatarsophalangeal; PIP = proximal interphalangeal.

Joints in grey only have to be assessed for the DAS44 joint count.

For tenderness, the examiner will exert pressure on each joint and grade the response as: not tender; tender on palpation; tender and patient winces; tender, patient winces, and patients tries to withdraw by pressure and joint manipulation on physical examination.

For the DAS44, the number of painful joints is calculated with the Ritchie Articular Index (RAI). The RAI is calculated as follows:

- For the jaw, sternoclavicular, and acromioclavicular: only the highest score of the right and left joint is counted
 - E.g. the right jaw is scored 1 and the left jaw is scored 2, then the pain score for the jaws is 2; the right sternoclavicular is scored 3 and the left sternoclavicular is scored 0, then the pain score for the sternoclaviculars is 3
- Complex joints are counted as one: of the MCP, PIP and MTP joints, only the highest score of the right joint and the highest score of left joint is counted
 - E.g. on the right hand the MCPI,II,IV are scored 1 and MCP III,V are scored 2, then the pain score for the MCPs on the right is 2 (pain score for the left hand is calculated separately); on the left foot the MTPI,II are scored 0, MTPIII is scored 3 and MTPIV,V are scored 1, then the pain score for the MTPs on the left is 3 (pain score for the right foot is calculated separately)
- For all other joints, the pain score is as indicated during assessment.

For the DAS28, no grades in tenderness will be used for the calculation of the tender joint count. All joints with a pain score of 1 or higher are counted as 1 painful joint.

Joint prosthesis, arthrodesis, or fused joints will not be taken into consideration for tenderness or swelling.

15.3 Appendix C:

Calculation of DAS28 and DAS44; EULAR response; ACR improvement

CALCULATION DAS28

DAS28 is calculated as follows:

$$\text{DAS28} = 0.56 * \text{sqrt}(\text{tender28}) + 0.28 * \text{sqrt}(\text{swollen28}) + 0.70 * \text{ln}(\text{ESR}) + 0.014 * \text{GH}.$$

CALCULATION DAS44

DAS44 is calculated as follows:

$$\text{DAS44} = 0.54 * \text{sqrt}(\text{RAI}) + 0.065 * (\text{swollen44}) + 0.33 * (\text{ln})\text{ESR} + 0.0072 * \text{GH}$$

Note: for both DAS44 and DAS28, the joint factors are adjusted in case of unevaluable joints.

E.g. left knee unevaluable due to knee prosthesis:

$$\text{DAS28} = (28/27)*0.56 * \text{sqrt}(\text{tender27}) + (28/27) * 0.28 * \text{sqrt}(\text{swollen27}) + \text{etc.}$$

EULAR RESPONSE CRITERIA FOR THE DAS28 AND DAS44

Current value of the DAS28	Current value of the DAS44	Improvement in DAS from baseline		
		>1.2	>0.6 - ≤1.2	≤0.6
≤3.2	≤2.4	good	moderate	none
>3.2 and ≤5.1	>2.4 and ≤3.7	moderate	moderate	none
>5.1	>3.7	moderate	none	none

Abbreviations: DAS28 = Disease activity score of 28 joints calculated with erythrocyte sedimentation rate; DAS44 = Disease activity score of 44 joints. ([Van Gestel 1996](#); [Van Gestel 1999](#))

ACR RESPONSE CRITERIA

American College of Rheumatology response score

≥20% improvement in tender joint count

≥20% improvement in swollen joint count

≥20% improvement in at least 3 of the following 5 measures:

- Patient's global assessment of disease activity
- Physician's global assessment of disease activity
- Patient's assessment of pain
- Disability
- Acute-phase reactant

([Felson 1995](#))

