6.2 Inclusion criteria

In order to be eligible to participate in this study, a subject must meet all of the following criteria:

- RA according to the 1987 or 2010 classification criteria of the American College of Rheumatology (ACR) and the European League Against Rheumatism (EULAR) ([Aletaha D 2010](#));
- inadequate disease control, as evidenced by a 28-joint disease activity score (DAS28) of ≥ 2.60 . For eligibility, the DAS28 can be calculated with ESR or CRP, and also recalculated from the DAS of 44 joints. A DAS28 may be calculated with clinical and lab assessments obtained no more than 4 weeks before the baseline visit.
- age ≥ 65 years.

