9.1.1 Main study outcomes

a) GC benefit/harm balance

Benefit

Primary outcome measure

- Signs and symptoms: the time-averaged mean value of the DAS28;

Secondary outcome measures

- Damage progression: 2-year change in total Sharp/van der Heijde damage score of hands and forefeet radiographs.
- WHO-ILAR core set of RA outcome measures, including pain, patient and physician global assessment, physical disability, joint counts (swollen joints and tender joints), acute phase reactants (C-reactive protein (CRP) and erythrocyte sedimentation rate (ESR)), and radiographs of hands and forefeet at 0 and 2 years
 - DAS28 is calculated is calculated from 4 of these
- Severity and duration of morning stiffness
- Fatigue
- SF36 - The Short Form 36-item Health Survey, a questionnaire about QoL
- RA Impact of Disease (RAID) tool – The RAID is a validated questionnaire assessing the seven most important domains of impact of RA on the patients
- Health Assessment Questionnaire (HAQ)
- cost questionnaire, including
 - Activity limitation (part of cost questionnaire)
 - Work disability (for those holding a paid job, part of cost questionnaire)
- Utility/Quality-adjusted life years (QALY): Euro-QoL in 5 dimensions (EQ-5D)

Harm

Primary outcome measure

The total number of patients experiencing at least one AE of Special Interest. An 'AE of Special Interest' is defined as either a SAE according to the GCP definition (described in chapter 10.2.2), or the occurrence of one the following AEs:

- any AE (except loss of efficacy, worsening of disease) that leads to the definite cessation of one of the antirheumatic drugs, including trial medication;

- a cardiovascular event (myocardial infarction, cerebrovascular event, peripheral arterial vascular event)
- newly occurring hypertension requiring drug treatment;
- newly occurring diabetes mellitus requiring drug treatment;
- symptomatic bone fracture requiring treatment;
- infection requiring antibiotic treatment;
- newly occurring cataract or glaucoma.

AEs can be reported spontaneously by patients, on prompting at clinic visits or by telephone interviews, and by the treating physician. The AEs specified above will be recorded with special care in a separate procedure. This procedure includes adjudication through the collection of evidence. This can be a declaration of the treating physician (in case of start of treatment), or a copy of a letter confirming the event, kept on file in the center.

Secondary outcome measures

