11. STATISTICAL ANALYSIS

11.1 Primary study outcome(s)

Benefit

The two primary outcomes for benefit are RA disease activity and progression of joint damage. Disease activity is operationalized as DAS28. This index comprises a formula that includes 28 tender and swollen joint counts, general health (GH; patient assessment of disease activity; Likert scale from 0-10 recoded to 0-100, with 0=best, 100=worst), plus levels of ESR (mm/h)). For calculation of DAS28, please see appendix C. Damage progression will be evaluated by the total Sharp/van der Heijde damage score of hands and forefeet (appendix D).

Primary analysis: DAS28

The DAS28 is a continuous variable. We will compute the “time averaged DAS28” based on the trajectories over time for each individual, as part of the repeated measures in the longitudinal design. Observations are included in the follow up time until end of trial or the occurrence of a protocol violation (i.e., GC co-interventions as outlined in section 7.2).

The term ‘repeated measures’ refers to data with multiple observations on the same sampling unit; in this case, the multiple observations are taken over time (10 visits) in 450 RA patients. To address the issue of covariation between measures on the same unit, linear mixed models will be fitted because they permit the covariance structure to be incorporated into the statistical model. After modelling the covariance structure, inference about fixed effects proceeds essentially as when using simple Analysis of Covariance (ANCOVA); i.e., enabling estimation of group effects “averaged over time” measured in DAS28-units. Using repeated-measures mixed models we will analyse mean trajectories in continuous end points. The model will include treatment (group), and the multiple stratification variables (participating study site, prior exposure to GC, and concurrent start of other anti-rheumatic therapy) as fixed effects, with the baseline value of the relevant variable as a covariate.

Secondary analyses: DAS28

Change in DAS28 over the first 3 months of the trial (when the chance of co-intervention is least) will be compared between the treatment groups by ANCOVA, adjusting for the level at baseline. In secondary analyses, observations in patients after the protocol violation will be included in the analysis described above.

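### The DAS28 correction for unevaluable joints puts the 28/27 factor outside the square root, which about doubles the adjustment; individual scores rise slightly and the treatment contrast hardly moves.

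*Protocol*

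**What the plan says.** Protocol Appendix C defines DAS28 as 0.56·sqrt(tender) + 0.28·sqrt(swollen) + 0.70·ln(ESR) + 0.014·GH, on 28 joints. A note adds that, for DAS28 and DAS44 alike, "the joint factors are adjusted in case of unevaluable joints". The only worked example is a left knee prosthesis: both joint coefficients are multiplied by 28/27, and the roots are taken of the unscaled 27-joint counts. Appendix B says which joints drop out: "Joint prosthesis, arthrodesis, or fused joints will not be taken into consideration for tenderness or swelling".

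The score carries weight. Protocol section 9.1.1 names the primary benefit outcome as "Signs and symptoms: the time-averaged mean value of the DAS28", and section 11.1 refers the reader on: "For calculation of DAS28, please see appendix C". Section 6.2 requires "inadequate disease control, as evidenced by a 28-joint disease activity score (DAS28) of" at least 2.60. The SAP gives no DAS28 formula of its own. Its rule for operated joints (SAP section 4.2) concerns only the radiographic damage score.

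**The concern.** The ratio 28/27 makes sense as scaling a count from 27 joints to 28. In DAS28 the count sits under a square root, so a factor placed in front of the root acts as if the count had been multiplied by (28/27) squared.

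The score is the primary benefit outcome. It also feeds the EULAR response (Protocol Appendix C), minimal disease activity at DAS28 below 2.6 (SAP Appendix A) and the -0.6 responder rule in the nonresponder sensitivity analysis (SAP section 4.2). Patients are 65 or older, and joint replacement is a recorded outcome. If a counted joint becomes unevaluable during follow-up, that patient's multiplier changes between visits, and the baseline covariate does not remove the step.

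**Working it through.** **Inputs.** The coefficients 0.56 and 0.28 and the factor 28/27 come from Appendix C. The 0.52 DAS28 contrast is the cited 3-month trial result in Protocol section 6.4. Joint counts, numbers of unevaluable joints and shares of patients affected are assumptions. Write m for unevaluable joints, r = 28/(28 - m), and T and S for the tender and swollen counts.

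**1. The plan's multiplier.** For m = 1, r = 28/27 = 1.0370, as in the example. Prorating the count gives sqrt(r·T) = sqrt(r)·sqrt(T), a multiplier of 1.0184. The written uplift is 3.7% and the prorated uplift 1.8%, a ratio of about 2.

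**2. Boundary check.** If every evaluable joint is tender and swollen, the corrected joint part should equal the 28-joint maximum, 0.84·sqrt(28) = 4.445.

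| m | as written | inside the root |
|---|---|---|
| 1 | 4.526 | 4.445 |
| 2 | 4.613 | 4.445 |
| 4 | 4.801 | 4.445 |

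For the tender term alone with m = 1, the values are 3.02 as written against 2.96.

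**3. Excess per score.** Excess = (r - sqrt(r))·(0.56·sqrt(T) + 0.28·sqrt(S)). The first bracket is 0.0187, 0.0392 and 0.0865 for m = 1, 2 and 4. The joint part is 1.188 at 2/2, 1.737 at 5/3 and 2.457 at 10/6.

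| T/S | m = 1 | m = 2 | m = 4 |
|---|---|---|---|
| 2/2 | 0.022 | 0.047 | 0.103 |
| 5/3 | 0.032 | 0.068 | 0.150 |
| 10/6 | 0.046 | 0.096 | 0.213 |

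With no tender or swollen joint the excess is zero.

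**4. Comparison with the full count.** In a simulation of 28 exchangeable joints (beta-binomial counts, m joints masked), the mean bias against the full 28-joint score was:

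| Mean T/S | m | no correction | as written | inside the root |
|---|---|---|---|---|
| 2/1.5 | 1 | -0.021 | +0.012 | -0.005 |
| 2/1.5 | 4 | -0.087 | +0.049 | -0.022 |
| 8/6 | 1 | -0.040 | +0.036 | -0.002 |
| 8/6 | 4 | -0.164 | +0.156 | -0.010 |

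At the higher counts the written rule is about as biased as no correction, with opposite sign. At the lower counts it beats no correction but is still worse than prorating.

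**5. Treatment contrast.** Let a share q of each arm have m unevaluable joints, and let the whole 0.52 lie in the joint terms, which is the worst case. The contrast then changes by 0.52·q·(r - sqrt(r)): 0.52·0.1·0.0187 = 0.001 at q = 10%, m = 1, and 0.52·0.3·0.0865 = 0.0135 at q = 30%, m = 4. At counts of 8/6, the group mean rises by 0.004 to 0.059 over the same range.

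**6. Thresholds.** Near 2.60 few joints are active. With one joint missing, a patient with 1 tender and 0 swollen joints gains 0.0187·0.56 = 0.010, and one at 2/2 gains 0.022. For change scores with the same m at both visits, a joint-term change of 0.6 is overstated by 0.6·0.0187 = 0.011 when m = 1.

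**The case against.** The case for leaving the rule alone is that the consequence is slight. The rule is the same in both blinded arms, baseline DAS28 is a covariate, and the worst-case change in the contrast above is about 0.01. The documents do not say how many patients have unevaluable joints. Their only example is a single knee, so four missing joints is a scenario and not a finding. Joints outside the 28-joint count, such as the hip, do not enter DAS28 at all. This all stands and limits the point to correct derivation.

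Three stronger readings are tempting and are not supported.

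- **Ineligible patients were materially admitted.** The larger excesses belong to patients well away from 2.60. At 10/6 with four joints missing, the prorated joint part alone is 2.457·1.080 = 2.65, above the threshold before ESR or GH is added. Section 6.2 also allows DAS28 by CRP or recalculated from DAS44. Neither formula is given, so no excess can be computed on those routes.
- **Scores leave the DAS28 scale.** The joint terms exceed their own maximum, but the stated range in Protocol section 9.3.5 is 0 to 9.4. With all 27 joints tender and swollen, ESR 100 and GH 100, the written formula gives 4.526 + 3.224 + 1.4 = 9.15.
- **The same repair fits DAS44.** The RAI is graded 0 to 3 and takes the highest score within joint groups. One unevaluable finger joint need not lower its maximum, so prorating by evaluable joints could itself over-correct.

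**Conclusion.** The algebra is certain: the written factor over-corrects, as Appendix C's own formula shows at the boundary, and nothing in the SAP replaces it. The size is small: about 0.02 to 0.05 DAS28 points for one missing joint at the assumed counts, and 0.1 to 0.2 for four.

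The effect on the mean treatment contrast is very small, about 0.001 to 0.014 on a contrast of 0.52 if 10 to 30% of patients in each arm have one to four unevaluable joints. A reader might infer a biased primary comparison; with one rule for both arms, the documents do not support that. What remains is slightly wrong individual scores, a few possible reclassifications at the response and disease-activity cut-offs, and a small artificial step when a counted joint becomes unevaluable mid-trial (about 0.03 excess at 5/3). Recruitment closed on 31 December 2018 (Protocol section 6.4), so admissions cannot change.

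**What to change.** In the SAP, define the DAS28 joint part as 0.56·sqrt(tender·28/n) + 0.28·sqrt(swollen·28/n), with n the number of evaluable joints at that visit. Recompute all DAS28 values and the outcomes derived from them on the stored counts. Report how many patients and visits have n below 28, and give the as-written version as a sensitivity analysis. State how the same adjustment is made in DAS28-CRP, which the SAP also uses.

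For DAS44, the swollen term is linear and may keep the outside factor. The RAI term should not be prorated by joint count until a denominator is defined that reflects its grouped, graded scoring.

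The cost is one line in the derivation program and a rerun. No new data are needed if the database holds the joint-level entries on the Appendix B form, and the change does not depend on treatment allocation.
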